6.3.4 Fourth Primary Estimand

Primary Objective 2: To assess the safety of FTC/TDF for PrEP during pregnancy and postpartum by comparing pregnancy outcomes and maternal and infant safety between cohorts.	
Estimand description	Incidence rate ratio of cumulative adverse events up to the age 26-week visit among PrEP exposed vs. PrEP unexposed infants
Treatment	
Infants exposed to the following maternal treatment in utero and/or through breastfeeding:
 
 1. Daily oral PrEP (200 mg FTC/ 300 mg TDF) throughout follow-up. 2. Enhanced adherence support, including SMS messaging and feedback of drug levels with tailored counseling. 3. Behavioral HIV risk reduction package
Target population	Analysis set
Infants born to women who are pregnant and HIV-uninfected, 16-24 years of age, with a confirmed singleton pregnancy of 32 weeks' gestation or less and who have access to a mobile phone and are able to receive and read SMS messages	Infant Safety Set: all enrolled infants
Variable(s)	Outcome measure(s)
Infant adverse events: 
 • Infant death within the first 26 weeks of life • Infant Grade 3 or higher adverse events reported between birth and the age 26-week visit. 	Outcome measures as defined by the variable (graded according to the NIAID DAIDS Table for Grading the Severity of Adult and Pediatric Adverse Events). The start of person-time for the PrEP-exposed group is birth for Cohort 1 and birth or Cohort 2/step 2 entry (whichever is later) for Cohort 2; The start of person-time for the PrEP unexposed group is birth (Cohort 2 participants only; person-time is censored when initiating PrEP for participants enrolled in Cohort 2/Step 2).
Handling of intercurrent events	Handling of missing data

 • Mother's failing to start PrEP (in Cohort 1 or Cohort 2/Step 2) (Treatment policy strategy) • Mother's discontinuation of PrEP (Treatment policy strategy) 	Participants who discontinue follow-up before the age 26-week visit will have their outcome determined based on data available until the time of discontinuation (i.e., a participant who discontinued follow-up without a prior AE is assumed not to have an AE had they been observed for the intended duration).
Population-level summary measure	Analysis approach

 • Incidence rate ratio (among PrEP exposed vs. PrEP unexposed infants) of cumulative adverse events up to the age 26-week visit 	
 • Incidence rate ratio of cumulative adverse events up to the age 26-week visit (among PrEP exposed vs. PrEP unexposed infants) estimated based on Poisson distribution (with 95% Wald CI).

Supplemental Analyses:

- Analyses will be repeated stratifying by time of infant drug exposure (i.e., antepartum (AP) and postpartum (PP), and within AP stratified by gestational age category of maternal enrollment).
- Rates of infant adverse events will also be calculated and compared across levels of maternal PrEP adherence (based on TFV-DP levels in dried blood spots). Models will be fit adjusting for potential confounders.
- To compare time to first infant adverse event in PrEP exposed vs. PrEP unexposed infants, the hazard ratio (95% CI) will be estimated with Logrank test p-value from Cox proportional hazards regression on time to first AE with PrEP exposure as a time-varying covariate.

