#### **Primary Objective 2.3.2:**

*Analyses of adverse pregnancy outcomes:* The proportion of women in Cohort 1 and Cohort 2 with adverse pregnancy outcomes (a composite indicator defined as at least one of the following: spontaneous abortion (occurring at <20 weeks gestation), stillbirth (occurring at  $\geq 20$  weeks gestation), preterm delivery (<37 completed weeks gestation), or small for gestational age (<10th percentile using INTERGROWTH-21st norms and ultrasound (US)- derived gestational age at delivery) will be estimated and compared. Univariable and multivariable logistic regression methods will be used to evaluate associations of PrEP use and the composite outcome indicating presence vs. absence of any adverse pregnancy outcomes, controlling for potential confounders. The same analyses will be conducted for each of the pregnancy outcomes which comprise the composite outcome separately.

*Analyses of maternal adverse events and infant adverse events:* Cumulative rates of maternal adverse events and infant adverse events will be compared, respectively, in Cohort 1 and Cohort 2. Where appropriate, there will be stratification according to time period (i.e., antepartum (AP) and postpartum (PP), and within AP by gestational age category of enrollment). Maternal adverse events will be considered separately from infant adverse events. Cox proportional hazards regression will be used to evaluate differences in the rate of adverse events in the two cohorts. For the maternal adverse events, among women in Cohort 1, person time will begin accruing when PrEP is initiated and for women in Cohort 2 it will begin accruing after study entry. Rates of maternal and infant adverse events in AP and PP periods will also be calculated and compared across levels of PrEP adherence (based on TFV-DP levels in DBS). Models will be fit adjusting for potential confounders.

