Incidence rate ratio (among PrEP exposed vs. PrEP unexposed women) of cumulative adverse events up to 26 weeks postpartum	Incidence rate ratio of cumulative AEs up to the week-26 postpartum visit (among PrEP exposed vs. PrEP unexposed women) estimated based on Poisson distribution (with 95% Wald CI).

Supplemental Analyses:

- Analyses will be repeated stratified by time period (i.e., antepartum (AP) and postpartum (PP), and within AP stratified by gestational age category of enrollment).
- Rates of maternal adverse events in AP and PP periods will also be calculated and compared across levels of PrEP adherence (based on TFV-DP levels in dried blood spots). Models will be fit adjusting for potential confounders.

- To compare time to first adverse event in PrEP exposed vs. PrEP unexposed women, the hazard ratio (95% CI) will be estimated with Logrank test p-value from Cox proportional hazards regression on time to first AE with PrEP exposure as a time-varying covariate.

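### The primary maternal and infant adverse-event rate ratios carry no term for infant age or pregnancy period, so switching in Cohort 2 confounds them with time whenever the event rate changes over follow-up

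*SAP*

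**What the plan says.** **Primary analyses.** For infants (SAP 6.3.4) the result is a rate ratio "among PrEP exposed vs. PrEP unexposed infants) estimated based on Poisson distribution (with 95% Wald CI"). For mothers (SAP 6.3.2) it is an "Incidence rate ratio of cumulative AEs up to the week-26 postpartum visit (among PrEP exposed vs. PrEP unexposed women) estimated based on Poisson distribution", again with a Wald interval. Neither primary analysis names a covariate or a time band.

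**Person-time.** For infants, exposed time starts as follows: "PrEP-exposed group is birth for Cohort 1 and birth or Cohort 2/step 2 entry (whichever is later) for Cohort 2". Unexposed time comes only from Cohort 2, starts at birth, and "person-time is censored when initiating PrEP for participants enrolled in Cohort 2/Step 2". For mothers, exposed time starts at study entry in Cohort 1 and at Step 2 entry in Cohort 2.

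**Switching.** SAP 2.1.2 lets Cohort 2 women start PrEP at any stage after entry. Under Protocol 5.3.2, counselling asks women not on PrEP whether they want to start.

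**Supplemental analyses.** Maternal analyses are repeated by antepartum and postpartum period. For infants, "Analyses will be repeated stratifying by time of infant drug exposure", which is not age at risk. Both estimands also have a Cox model for first AE with time-varying exposure, whose time scale is not named.

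**Protocol.** Section 3.2 bases the primary analysis on the cohort chosen at baseline. Section 9.2.6 states: "Cox proportional hazards regression will be used to evaluate differences in the rate of adverse events in the two cohorts".

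**The concern.** A single Poisson rate ratio compares total events over total person-time, which is fair only if both groups spend similar shares of their time at each level of risk. Here the allocation rule prevents that for switchers. If a mother starts PrEP postpartum, her infant's first weeks are always unexposed and the later weeks always exposed. The unexposed group is then enriched with early time and the exposed group with late time.

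If AEs concentrate in the first weeks of life, the unexposed rate rises and the exposed rate falls with no drug effect at all. The SAP's hypothesis is that AE rates are higher with PrEP, so a downward shift in the infant ratio could mask part of an excess. The size would depend on how many women switch and when, which the analysis does not control.

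**Working it through.** **1. The plan's own figure.** The documents state no expected rate ratio. The nearest AE comparison is Protocol Table 10: 10% in Cohort 2 (n=100) against 23% in Cohort 1 (n=200), 80% power, alpha 0.05.
- Pooled proportion: (200×0.23 + 100×0.10)/300 = 0.1867.
- Null SE: √(0.1867×0.8133×(1/200 + 1/100)) = 0.0477.
- Alternative SE: √(0.23×0.77/200 + 0.10×0.90/100) = 0.0423.
- z = (0.13 − 1.96×0.0477)/0.0423 = 0.86, so power is 80.6%.

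The table reproduces. It compares proportions between fixed groups and does not bear on the allocation of time.

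**2. Infants, no PrEP effect.**
- From the documents: 200 and 100 infants, 26 weeks of follow-up, the person-time rule above.
- Assumed: 0.10 expected events per infant in weeks 0-4 (0.025 per week) and 0.05 in weeks 4-26 (0.00227 per week); postpartum switches spread evenly over weeks 2-20.

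For each postpartum switcher:
- Mean time moved to exposed: 26 − 11 = 15 weeks.
- Mean events moved: [0.025×2²/2 + 0.05×2 + 0.00227×(22² − 6²)/2]/18 = (0.05 + 0.10 + 0.509)/18 = 0.0366.

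At 30% switching (30 infants, 1.10 events and 450 weeks moved):
- Exposed: (30 + 1.10)/(5,200 + 450) = 0.00550 per week.
- Unexposed: (15 − 1.10)/(2,600 − 450) = 0.00647 per week.
- Ratio: 0.85.

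The common true rate is 0.15/26 = 0.00577. The exposed rate is about 5% too low and the unexposed rate about 12% too high, so most of the shift is on the unexposed side.

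If half of those 30 switch before birth, 15 infants move whole (2.25 events, 390 weeks) and 15 move in part (0.55 events, 225 weeks):
- Exposed: 32.80/5,815 = 0.00564.
- Unexposed: 12.20/1,985 = 0.00615.
- Ratio: 0.92.

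| Expected ratio with no effect | 10% switch | 30% | 50% |
|---|---|---|---|
| Risks 10% then 5%, all switches postpartum | 0.95 | 0.85 | 0.75 |
| Same risks, half before birth | 0.97 | 0.92 | 0.85 |
| Risks 8% then 8%, all postpartum | 0.97 | 0.90 | 0.82 |
| Same risks, half before birth | 0.98 | 0.94 | 0.89 |
| Flat rate, or all switches before birth | 1.00 | 1.00 | 1.00 |

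In a separate calculation with a weekly rate half as high in the first 4 weeks as later, 30% switching gives 1.03 (switch at week 6) or 1.02 (week 14). The direction follows the assumed shape of the rate.

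**3. Mothers, no PrEP effect, 30% switching.** Assumed: 5% antepartum, 8% in the two weeks around delivery, 3% later; delivery 16 weeks after entry, so 42 weeks in all.
- *Antepartum switches, spread over weeks 2-16.* Mean time moved is 33 weeks. Mean events moved are [(0.05/15)×13²/2 + 0.11×13 + 0.06 + 0.03]/14 = 0.1287. Exposed (32 + 3.86)/(8,400 + 990) = 0.00382; unexposed (16 − 3.86)/(4,200 − 990) = 0.00378; ratio 1.01.
- *Postpartum switches, spread over weeks 2-20.* Mean time moved is 15 weeks; mean events moved are 0.03×15/25 = 0.018. Exposed 32.54/8,850 = 0.00368; unexposed 15.46/3,750 = 0.00412; ratio 0.89.

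With delivery 12 to 20 weeks after entry, the same formulas give about 0.99-1.03 for antepartum and 0.88-0.91 for postpartum switching.

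**4. Against sampling error.** At 15 events per 100 infants, 30 and 15 events give a Wald factor of exp(1.96×√(1/30 + 1/15)) = 1.86 either way. A 3-5% shift at 10% switching is small beside that.

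**5. Effect of the fix.** Take an infant rate five times higher in weeks 0-4, 30% switching at week 6 and about 15 events per 100. The crude ratio is 0.862 (95% CI 0.452 to 1.646). With an age-band term it is 1.000 (0.522 to 1.916). Interval width on the log scale goes from ln(1.646/0.452) = 1.29 to ln(1.916/0.522) = 1.30. The adjusted value is exactly 1 because the band edge matches the assumed change in rate; a rate that varies within bands would leave a smaller residual.

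**The case against.** **The bias is conditional.** It needs a changing AE rate and, for infants, postpartum switchers. The documents supply neither figure. Protocol 7.2.2 counts conditions found during and after birth as AEs, but that is a recording rule and does not show that events cluster early. This stands, and it is why the sizes above are scenarios.

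**The plan already has mitigation.** It has the maternal antepartum/postpartum repeat, the time-varying Cox models, and a planned report of the frequency and timing of switching (SAP 7). A careful reader could detect a distortion. This stands in part: all of it sits beside a primary estimate that stays crude, and the infant stratification is not by age at risk.

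**Precision is low and the aim descriptive.** Protocol 9.2.1 says power for safety conclusions is limited. That lowers the priority, but a wide interval does not correct a shifted centre.

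**Stronger readings that the documents do not support:**
- *Both ratios are biased toward PrEP looking safe.* For mothers, an antepartum switch carries delivery into exposed time and can push the ratio above 1.
- *The fault lies in replacing Cox with Poisson.* Protocol 9.2.6 compares the two cohorts, and Section 3.2 fixes cohort at baseline. The problem does not arise there because switchers are not moved, whichever model is fitted.
- *The infant postpartum-exposure stratum is far more distorted still.* The SAP does not say which infants form that stratum or which unexposed time is its comparator, so no size can be put on it.

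**Conclusion.** The concern holds in conditional form. Both primary AE ratios are confounded by time since birth or entry whenever the AE rate changes over follow-up, because switchers' exposed time is always later than their unexposed time and no time term is named.

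For infants the ratio falls below 1 under no effect if the rate declines after the neonatal period and mothers switch postpartum. In the 10%-then-5% scenario with all switches postpartum, a true ratio of about 1/0.85 = 1.17 would appear as 1.0 at 30% switching, and about 1/0.75 = 1.33 at 50%. For mothers the direction depends on switch timing.

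A reader might infer that the ratio must fall below 1 if PrEP does nothing. It need not: a flat rate gives 1.00 and a rising rate gives a value above 1. The real size is unknown. This should be fixed before the analysis, but the documents do not show that the primary result will mislead.

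**What to change.** - **SAP 6.3.2 and 6.3.4:** split person-time into bands. Infants: 0-28 days, 29 days to 14 weeks, 14 to 26 weeks. Mothers: antepartum, delivery to 6 weeks, later postpartum. Fit the Poisson model with exposure, band as a factor, and log person-time as offset. Report the band-adjusted rate ratio as primary and the crude ratio as secondary.
- **Supplemental Cox models:** state the time scale (infant age; for mothers, time relative to delivery or since entry).
- **Infant stratification by time of exposure:** define the strata. In any stratum of first exposure postpartum, compare only with unexposed person-time at the same infant ages.
- **Grouping:** reconcile the SAP's exposure-based groups with Protocol 3.2, which bases the primary analysis on original cohort.

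Cost: SAP wording and a few lines of code, with no new data. The interval becomes slightly wider. The bands should be fixed before results are seen.

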6.3.5 Fifth Primary Estimand

Primary Objective 2: To assess the safety of FTC/TDF for PrEP during pregnancy and postpartum by comparing pregnancy outcomes and maternal and infant safety between cohorts.	
Estimand description	Difference in mean infant growth and development outcomes at birth and age 26 weeks among PrEP exposed and PrEP unexposed infants;
Treatment	Infants exposed to the following maternal treatment in utero and/or through breastfeeding: 
1. Daily oral PrEP (200 mg FTC/ 300 mg TDF) throughout follow-up.2. Enhanced adherence support, including SMS messaging and feedback of drug levels with tailored counseling.3. Behavioral HIV risk reduction package
Target population	Analysis set
Infants born to women who are pregnant and HIV-uninfected, 16-24 years of age, with a confirmed singleton pregnancy of 32 weeks' gestation or less and who have access to a mobile phone and are able to receive and read SMS messages	Infant Safety Set: growth and development Infants of women who have ever used PrEP (in Cohort 1 or Cohort 2 Step 2) will be considered PrEP exposed. Infants of women who have never used PrEP will be considered PrEP unexposed. If PrEP exposure occurs prior to the outcome measurement of interest then the infant will be considered PrEP exposed.
Variable(s)	Outcome measure(s)
Infant growth and development outcomes	The following will be calculated to evaluate infant safety outcomes: 
• Infant bone mineral content (grams) by dual energy X-ray absorptiometry (DXA) scan of the whole body (WB-BMC) at birth and lumbar spine (LS-BMC) at birth and 26 weeks• Infant creatinine and CrCl rate measured by Schwartz equation at birth and at 26 weeks• Infant length-for-age z-score at birth and at 26 weeks The week 26 measurement will be at the Week 26 study visit

Handling of intercurrent events	Handling of missing data

• Mother's failure to start PrEP (in Cohort 1 or Cohort 2/Step 2) (Treatment policy strategy)• Mother's discontinuation of PrEP (Treatment policy strategy)	Sensitivity analysis: for infants discontinuing study prior to the 26 weeks of age, use the last value carried forward for the 26 weeks visit.
Population-level summary measure	Analysis approach
Difference in mean infant growth and development outcomes between PrEP exposed (in Cohort 1 and Cohort 2 step 2) and PrEP unexposed infants (infants in Cohort 2) at birth and 26 weeks of age	Means will be estimated and compared between PrEP-exposed and PrEP unexposed infants using two sample t-tests at each time point of evaluation, or Wilcoxon rank sum tests as appropriate to evaluate differences in these endpoints between PrEP-exposed and PrEP unexposed infants.

7. Report Contents

An overview of the contents of the final analysis report for the PrEP Comparison Component is outlined below. Additional details of the final analysis report contents are provided in the AIP.

- CONSORT diagram
- Study entry:
 - Screening
 - Accrual
 - Eligibility
- Baseline characteristics (reported in ClinicalTrials.gov)
 - Maternal characteristics at baseline
 - Infant characteristics at birth
- Study retention (reported in ClinicalTrials.gov)
 - By Cohort and study visit
- Treatment status:
 - By Cohort (Cohort 1-PrEP, Cohort 2-No PrEP)
 - Frequency and Timing of switching from No PreP to PrEP (i.e., Cohort 2 step change)
- PrEP discontinuation, and PrEP restart (if applicable)
 - PrEP discontinuation reasons
- PrEP adherence:
 - N (%) with optimal adherence at each visit, overall, during pregnancy, and postpartum, and by gestational age group at enrollment
 - Number and timing of visits missed when assessment of PrEP adherence was expected
- Maternal safety outcomes
 - By PrEP exposure
 - During pregnancy and postpartum
- Pregnancy Outcomes
 - Overall and by PrEP exposure
- Infant safety outcomes
 - Overall, by PrEP exposure

8 Associated Documents

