### 6.4.2.2 Infant Procedures at Early Study Discontinuation

PrEP Comparison Component Infant Early Study Discontinuation Procedures		
Clinical		
 
• Perform complete infant physical exam
 
• Obtain interim medical/medications history including feeding history
 

Laboratory	Blood	
Collect blood for:
 
 
• Creatinine
 

	Other	
 
• Rectal swabs or fresh stool for microbiome
 

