#### **6.14 Infant DXA Scans**

Infants in the PrEP Comparison Component will undergo DXA scans of the whole body and lumbar spine at their Birth Visit and of the lumbar spine Week 26 postpartum. Scans will be performed according to standardized procedures described in the study-specific MOP. Scan images will be transferred electronically for centralized reading and results will be transmitted electronically from the central readers to the Data Management Center (DMC). The centralized readings of all scans will be made available to the study sites after the last scan has been read centrally. However, if an infant experiences a bone fracture subsequent to his or her scan, the result of his or her scan will be provided to the site as soon as available.

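### The only stated missing-data method for the infant growth and development estimand, a last-value-carried-forward sensitivity analysis, puts newborn lumbar-spine scans in place of 26-week scans and so cannot test robustness

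*SAP*

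**What the plan says.** The missing-data cell of SAP 6.3.5 has one entry. It is labelled a sensitivity analysis and says, of infants who leave the study early, to "use the last value carried forward for the 26 weeks visit". The same table says "The week 26 measurement will be at the Week 26 study visit", and the analysis cell compares exposure groups by t-test or Wilcoxon test at each time point. No rule is written for infants without a Week 26 value in that main comparison.

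One outcome is bone mineral content in grams, by "scan of the whole body (WB-BMC) at birth and lumbar spine (LS-BMC) at birth and 26 weeks". Also analysed at both ages are creatinine, CrCl by the Schwartz equation, and the length-for-age z-score.

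On collection, Protocol 6.14 schedules "DXA scans of the whole body and lumbar spine at their Birth Visit and of the lumbar spine Week 26 postpartum". The table "PrEP Comparison Component Infant Early Study Discontinuation Procedures" in Protocol 6.4.2.2 lists a complete examination, histories, creatinine and a microbiome sample, but no DXA. Appendix IIC agrees. Protocol 6.4 asks sites to make every effort at that visit, and lets them skip any evaluation done in the previous 30 days. Protocol 6.13 requires length at every infant visit.

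**The concern.** A sensitivity analysis is useful if it replaces the missing values under an assumption that could plausibly be true. Carrying a newborn scan to 26 weeks assumes that the infant's spine gained no mineral in between. LS-BMC is analysed in raw grams, and Protocol 8.1.4 says no infant normal ranges are in current use, so no age standardisation corrects for this.

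The outcome is a primary safety measure in self-selected cohorts, and this is the only missing-data check planned for it. If the carry-forward result disagrees with the main result, the cause may be only the number of newborn values in each group. If a real deficit shrinks, the analysis gives false reassurance. If exposed infants leave more often, it can suggest a bone effect that does not exist.

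**Working it through.** **1. What can be carried forward**

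| Outcome | Scheduled | At early discontinuation | Value carried to 26 weeks |
|---|---|---|---|
| LS-BMC | Birth, Week 26 | No | Always the birth scan |
| Creatinine, CrCl | Birth, Week 26 | Creatinine and length, best effort | Discontinuation value if obtained, otherwise birth |
| Whole-body BMC | Birth | No | None; no 26-week comparison |
| Length-for-age z-score | Birth, Weeks 6, 14, 26 | Yes | Latest length, already standardised for age |

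**2. The plan's own figure.** Protocol Table 11 gives 81% power for 0.35 SD with 200 and 100 infants. Two-sided at 0.05: 0.35/√(1/200 + 1/100) = 2.858, and Φ(2.858 − 1.960) = 81.5%. It reproduces. Table 11 concerns whole-body BMC at birth, so it is only a yardstick for LS-BMC at 26 weeks.

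**3. Shift in means.** Let k be the ratio of the 26-week mean μ to the birth mean, and d the proportion carried forward in a group. The group mean becomes (1 − d)μ + dμ/k. With no true effect, exposed minus unexposed is (d_unexposed − d_exposed)(1 − 1/k)μ. For 10% exposed and 20% unexposed:

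- k = 1.5: 0.10 × 0.333 = 3.3% of μ
- k = 2: 0.10 × 0.500 = 5.0%
- k = 3: 0.10 × 0.667 = 6.7%

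Reversing the dropout rates reverses the sign. With equal dropout the shift is zero.

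**4. SD inflation.** With a proportion p carried and the same coefficient of variation (CV) at both ages, the variance in units of μ² is (1 − p)CV² + p·CV²/k² + p(1 − p)(1 − 1/k)². Example, p = 0.15, k = 1.5, CV = 20%: 0.0340 + 0.0027 + 0.0142 = 0.0508 (unrounded terms), against 0.0400; the SD ratio is √1.271 = 1.13. The 26% CV is 16.6/63.8 from Table 11, used as a proxy.

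| k | CV 20% | CV 26% |
|---|---|---|
| 1.5 | +13% | +6% |
| 2 | +30% | +17% |
| 3 | +51% | +31% |

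**5. Effect on the test.** Let G be the rise from birth to 26 weeks in SD units, G = (1 − 1/k)/CV. For k from 1.5 to 3, G is 1.7 to 3.3 at a 20% CV and 1.3 to 2.6 at 26%. Take 233 and 117 infants (the enrolled numbers of women), SD 1 at both ages, and a true effect of −0.35 SD arising after birth.

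| Dropout exposed / unexposed | True effect | Estimate, G = 1 / 2 / 3 | Rejection rate, G = 1 / 2 / 3 |
|---|---|---|---|
| 15% / 15% | −0.35 | −0.30 at each G | 71% / 59% / 45% |
| 10% / 20% | 0 | +0.10 / +0.20 / +0.30 | 13% / 30% / 43% |
| 10% / 20% | −0.35 | −0.22 / −0.12 / −0.02 | 43% / 13% / 5% |
| 20% / 10% | 0 | −0.10 / −0.20 / −0.30 | 13% / 31% / 46% |

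The first estimate is 0.85 × (−0.35) = −0.30. Simulated t-tests for a subset of these cases agreed with the analytic rates within about 3 points. Observed 26-week values alone give 81% power with 15%/15% dropout and 80% with 10%/20%, without carry-forward bias if dropout is unrelated to the outcome.

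**The case against.** The strongest reply is that the rule is labelled a sensitivity analysis. A reader of the carry-forward clause alone might infer that newborn values enter the main 26-week comparison. The documents do not support that: the label comes first, the Week 26 measurement is tied to the Week 26 visit, and the natural reading of the main analysis is observed values. This stands, and it limits the point to the robustness check.

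Two other broad readings also fail. One is that a carried CrCl is always a newborn value. Creatinine and length are collected at early discontinuation, so the value may be later than birth. It is still not a 26-week value, and the birth value remains when the visit is missed or falls within 30 days of the birth sample. The other is that bone mineral content as a whole is affected; whole-body BMC has no 26-week value.

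The sizes are also open to challenge. The growth ratio, the 20% CV and the split dropout are not in the documents. The 15% attrition in Protocol 9.2.4 is maternal, counts from enrolment and is not split by cohort. Women lost before delivery contribute no infant birth value, so the carried share is probably lower. With 5% carried and a 26% CV, SD inflation is 2% to 13%. At that CV the spurious mean difference is 0.13 to 0.26 SD (0.033/0.26 to 0.067/0.26), below the 0.35 SD of the sample-size section. No document predicts dropout that differs by exposure. The SAP also leaves detail to an Analysis Implementation Plan that is not among the documents. These points reduce the likely size, but they do not make a birth scan a reasonable substitute for a six-month scan.

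**Conclusion.** The point holds fully for LS-BMC: carry-forward there can use only the birth scan, so the planned check is uninformative and may mislead. It holds less strongly for creatinine and CrCl, for which no size can be given because the documents contain no values at either age. The length-for-age z-score is much less affected.

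Dilution of an effect arising after birth, and SD inflation, occur even with equal dropout. A false difference in means requires dropout that differs by exposure. The figures illustrate the mechanism under assumed growth, variability and dropout; they do not forecast this trial. Because the main estimate is not affected by the text as written, this is a correction to the SAP that should be made, not a threat to the primary result.

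**What to change.** Amend SAP 6.3.5 as follows.

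1. State that the main 26-week comparison uses observed Week 26 values.
2. For LS-BMC, creatinine and CrCl, replace carry-forward in the sensitivity analysis by multiple imputation of the 26-week value from the birth value, gestational age at birth, sex, site, exposure, and length and weight at Weeks 6 and 14. A likelihood-based model of the birth and 26-week values is a simpler alternative. It is not equivalent, because it omits the intermediate growth data.
3. Report the number and proportion of missing 26-week values by exposure group for each outcome.
4. Keep carry-forward, if wanted, for the length-for-age z-score only.

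The cost is SAP wording and modest programming. All inputs are already collected; no visit or procedure changes.
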